1. SYNOPSIS

Study Title	Investigating non-invasive brain stimulation to enhance fluency in people who stutter
Internal ref. no. / short title	INSTEP Trial
Study Design	Double-blind randomised controlled trial. Active treatment: bi-hemispheric tDCS, Control: Sham tDCS. Minimisation randomisation.
Study Participants	Healthy adult males with developmental stuttering and healthy male controls with no speech disorders
Planned Sample Size	70 (40 participants with developmental stuttering, 30 control participants)
Planned Study Period	1 st November 2017 – 30th April 2020
	Outcome Measures
Primary	Change from baseline (i.e. baseline subtracted) in a clinical measure of stuttering severity (SSI-4), post training (1 week, 6 weeks, and 3 months after training).
Secondary	Change from baseline (i.e. baseline subtracted) in: (i) % disfluent syllables produced during conversation; (ii) % disfluent syllables produced during reading post training (1 week, 6 weeks, and 3 months after training). (iii) total score on an attitudinal measure (OASES), post training (6 weeks, and 3 months after training).
Other Pre-specified	Change from baseline (i.e. baseline subtracted) in: (i) total score on the Premonitory Awareness in Stuttering Scale; (ii) total score on the Beck Anxiety Inventory; (iii) subjective and objective ratings of stuttering severity and naturalness, post training (1 week, 6 weeks, and 3 months after training). Changes from baseline (i.e. baseline subtracted) % disfluent syllables produced during (i) conversation and (ii) reading, during the 5-day training (immediately post intervention days 1 to 5; immediately pre-intervention days 2 to 5).
	Exploratory (non-behavioural) measures
Other	We will use MRI and TMS, to evaluate neural structure, function, and excitability in people who stutter and in healthy controls. Using MRI, we will also obtain images of the vocal tract during speech. These measurements will be obtained just before training begins and 1 week after the end of the training in people who stutter and once only in healthy controls.

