4. STUDY DESIGN

This is a double-blind, placebo-controlled (sham tDCS), randomised trial, with 20 participants with developmental stuttering recruited for each arm of the trial. The participants will be expected to complete at least two visits to the OHBA imaging centre in Oxford (at baseline and at the +1 week follow up) for the assessments of neural structure, function, and to assess movements of the vocal tract (MRI, TMS, & vocal tract imaging). In addition, participants will complete one live interaction and one videoconference at baseline and at +1 week follow up, complete training for 5 days, and engage in two more videoconference interactions for follow-ups (6 weeks and 3 months after the end of training), which will involve doing reading and conversation tasks so speech fluency can be assessed. The researchers can travel to the participant's home or office for the live components of these visits as well as the tDCS + speech fluency training. In total, participants will have 9 visits over a 5-month period. A flowchart illustrating the study design is included in Appendix A.

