6.1. Screening and Eligibility Assessment

When a person who stutters contacts the research team and expresses a desire to participate, they will be sent the PIS outlining the procedures and risks involved in taking part. Screening will take place before volunteers have consented to take part in the study. The screening procedure involves obtaining information in line with tDCS, TMS, and MRI safety guidelines (outlined in the standard operating procedure documents developed within the Medical Sciences Division). Also see exclusion criteria in section 6.3 of this protocol. Screening criteria will be assessed by self-report.

Volunteers will also complete a screening assessment of stuttering severity to ascertain eligibility. In the first instance, one of the named investigators will conduct a screening by videoconference (Skype) to determine severity. Stuttering symptoms are typically increased on the first meeting (when participants are unfamiliar with their conversation partner) and over the telephone/ during videoconferencing. Consequently, if stuttering is determined to be of mild severity at this stage, the volunteer will be informed that they do not meet the inclusionary criteria for the study. If stuttering is of mild-moderate or greater severity, a face-to-face appointment will be scheduled, which will take place on University premises, or at the participant's home or office. The severity of stammering as ascertained on this visit will be used to determine whether participants should be enrolled into the study. If stuttering is of mild-moderate or greater severity, then they will be invited to participate.

Once we have determined eligibility, informed consent will be obtained and a suitable appointment will be scheduled, within three months of the screening. If the participant is deemed ineligible, we will first enquire if they wish to participate in other studies within the lab for which they might be eligible. If they do not, all screening data will be deleted (within a month of notification of ineligibility).

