6.4. Baseline Assessments

Following the screening to determine eligibility, participants will complete the baseline assessments (Visit 1, Days 1-2). This visit will take place at OHBA.

During this visit, we will obtain informed consent. We will obtain behavioural measures of speech fluency, as well as complete clinical assessments (SSI-4, OASES). Following this, participants will complete the brain and vocal tract imaging assessments (MRI and TMS) as described below.

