6.5. Subsequent Visits

Visits 2-6 [Days 3-7]

These visits may take place at University testing facilities, or at the participant's home or office and will take place at the same time on each day. Participants will complete a short speech fluency assessment during reading and conversation at the start and end of the session; this assessment will be video recorded. A safety screening for tDCS will be conducted to ensure that the participant is not experiencing any discomfort/ risk, and to check that eligibility has not been compromised (for example, by use of medication). The intervention will then be delivered (sham vs. true tDCS + speech fluency training). The speech fluency training lasts approximately 40 minutes and stimulation is delivered for 20 minutes at the start of the training. Each session should last no more than one hour on each of the five days of intervention.

Visit 7 [Days 14-15]:

This visit will take place at OHBA. We will obtain behavioural measures of speech fluency, as well as complete clinical assessments (SSI-4). Following this, participants will repeat the brain and vocal tract imaging assessments (MRI and TMS) described. Standard operating procedures and safety guidelines for each of these procedures will be followed.

Visit 8 [+6 weeks following Visit 6]

This visit will be conducted via videoconference. We will obtain behavioural measures of speech fluency, as well as complete clinical assessments (SSI-4, OASES).

Visit 9 [+3 months following Visit 6]

This visit will be conducted via videoconference. We will obtain behavioural measures of speech fluency, as well as complete clinical assessments (SSI-4, OASES).

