The primary outcome measure for the trial is the change in stuttering severity, measured using the Stuttering Severity Instrument, version 4 (SSI-4, Riley, 2009). Change from baseline score will be calculated (by subtraction of the baseline) at one week, 6 weeks and 12 weeks following the intervention. Change scores will be entered into a mixed model analysis of variance (ANOVA), with stimulation group (tDCS, sham) as the between subjects factor and speaking task and time point (1 week, 6 weeks, 12 weeks) as the within subjects factor. If a significant interaction between stimulation group and time point is found, separate repeated measures ANOVAs will be performed for each stimulation group or with three planned comparisons between groups at each time point.

Secondary outcome measures

We have three secondary outcome measures:

- i. Change from baseline score in percentage of disfluent syllables, during reading.
- ii. Change from baseline score in percentage of disfluent syllables, during conversation.
- iii. Change in total score on Overall Assessment of a Speaker's Experience of Stuttering (OASES).

Change in percentage of disfluent syllables will be calculated by subtraction of the baseline percentage for reading and conversation separately at one week, 6 weeks and 12 weeks following the intervention. Data will be analysed as described above for the primary outcome measure. Anticipating a significant effect of group in both measures, we will also compare the changes in reading with those in conversation at each time point separately for the tDCS group.

To test for the effects on the OASES measure, we will use a mixed model ANOVA with stimulation group (tDCS, sham) as the between subjects factor and time point (6 weeks, 12 weeks). We will not collect data at the 1-week post-intervention time-point to avoid violating test-retest validity of the scale. If a significant

interaction between stimulation group and time point is found, separate planned comparisons between groups will be performed for each time point.

Other pre-specified measures

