We are including the Beck Anxiety Inventory to monitor for any differences in anxiety between the groups, which should be minimized at baseline by the randomization procedure. Any effect of the intervention of stuttering severity may also have consequences for anxiety. We will assess the change in anxiety scores with the same analysis as planned for the primary outcome measure. We will also examine the correlation of the change in anxiety score and the change in (i) stuttering severity (SSI-4), and percentage of disfluent syllables on (ii) reading and (iii) conversation tasks

The Premonitory Awareness in Stuttering Scale (PAiS) tests for anticipation of stuttering events. We have included this as an exploratory measure. We also include subjective ratings of stuttering severity and speech naturalness, and an objective measure of speech naturalness. For each scale (PAiS, subjective severity, subjective naturalness, objective naturalness) change scores will be analysed as described for the primary outcome measure.

In addition, we include exploratory analysis of the effects of tDCS during the intervention period. Effects of tDCS immediately after intervention will be analysed using change in percentage of disfluent syllables (baseline subtracted) measured post-intervention on each day, for both reading and conversation. A mixed model ANOVA will be used with stimulation group (tDCS, sham) as the between subjects factor and time point (day 1 to 5) and task (reading, conversation) as the within-subjects factors. Carry-over of effects following a period including sleep will be analysed using change in percentage of disfluent syllables (baseline subtracted) measured immediately before the intervention, for both reading and conversation. A mixed model ANOVA will be used with stimulation group (tDCS, sham) as the between subjects factor and time point (day 2 to 5) and task (reading, conversation) as the within-subjects factors. The Day 1 time point will be omitted in this analysis, as no intervention will have been performed prior to that measurement.

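### The untreated Day 1 pre-session speech sample has no planned use; averaging it into the baseline of the two exploratory training-week analyses would gain precision at almost no cost

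*SAP*

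**What the plan says.** Protocol section 6.5, on training Visits 2-6: "Participants will complete a short speech fluency assessment during reading and conversation at the start and end of the session". Appendix B marks live speech at each of these visits, and section 6.6 has the recordings scored offline. So a live reading and conversation sample exists from the start of Visit 2, before any real or sham current.

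The synopsis lists the training-period measures as "immediately post intervention days 1 to 5; immediately pre-intervention days 2 to 5". The SAP (Other pre-specified measures) analyses post-session change over days 1 to 5. It analyses pre-session change, as carry-over, with "time point (day 2 to 5) and task (reading, conversation) as the within-subjects factors", and gives the reason for starting at day 2: "The Day 1 time point will be omitted in this analysis, as no intervention will have been performed prior to that measurement".

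Both analyses use baseline-subtracted values. For the follow-up outcomes the SAP says only "Change in percentage of disfluent syllables will be calculated by subtraction of the baseline percentage for reading and conversation separately", without naming the visit or mode of that baseline. The one visit labelled baseline is Visit 1. Protocol section 6.4 says "participants will complete the baseline assessments (Visit 1, Days 1-2). This visit will take place at OHBA". Section 4 says "participants will complete one live interaction and one videoconference at baseline and at +1 week follow up", and allows the live parts at the participant's home or office. Training visits may be at University facilities, home or office (section 6.5).

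**The concern.** The reason for leaving Day 1 out of the carry-over outcomes, that nothing had yet been delivered, is the same property that would make it a usable baseline. It is taken after randomisation but before stimulation and under blinding, so treatment cannot have affected it. No analysis uses it as a baseline, a covariate or a sensitivity check.

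Because the SAP works with raw change scores, all the error in the subtracted baseline passes into every change score. With 20 per arm that matters. There is also a question of context. The protocol accepts that stuttering varies with circumstances: "Stuttering symptoms are typically increased on the first meeting (when participants are unfamiliar with their conversation partner" (section 6.1, Screening and Eligibility Assessment). If the Visit 1 live sample is taken at OHBA and training happens at home, change during the training week includes a change of place. The Day 1 pre-session sample belongs to the training visits and would partly offset that.

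**Working it through.** **The plan's own figure.** Protocol section 9.2 gives 20 per arm for an effect size of 0.9, 80% power and a 5% error rate. Two-sided normal approximation: 2 × (1.96 + 0.84)² / 0.9² = 19.4, so 20 per arm. A two-sided t-test with 20 per arm has 79.2% power. The figure reproduces and is not in dispute.

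**Which baseline is planned.** Visit 1 is the only visit with that label. If the Day 1 pre-session sample were the subtracted baseline, its change would be zero by construction; the SAP gives a different reason for omitting it. Visit 1 is therefore the likely reading, but it is an inference.

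**Main calculation.** The documents give no SD or between-session correlation for % disfluent syllables. Assume equal variance σ² and equal correlation ρ between all occasions. For the mean of m later samples minus the mean of b baseline samples, within one task:

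Var = σ²(1 − ρ)(1/m + 1/b)

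The factor σ²(1 − ρ) cancels from ratios, so the percentages hold for any ρ.

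| Later samples | b = 1 | b = 2 | Variance cut | SE cut |
|---|---|---|---|---|
| One time point (m = 1) | 2.00 | 1.50 | 25% | 13% |
| Mean of days 2-5 (m = 4) | 1.25 | 0.75 | 40% | 23% |
| Mean of days 1-5 (m = 5) | 1.20 | 0.70 | 42% | 24% |

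**Illustration in power terms.** With 20 per arm, one time point and effect sizes in single-baseline SD units, power at 0.9 goes from 79.2% to 89.3%, and at 0.50 from 33.8% to 42.9%. The protocol's effect sizes of 0.93 and 0.50 are for the SSI, so this shows scale only.

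**Unequal correlations.** Take σ² = 1. Let the two baselines correlate r with each other and s with a later sample. At one time point the variance goes from 2 − 2s to 1 + (1 + r)/2 − 2s.
- r = 0.8, s = 0.6: 0.80 to 0.70, a cut of 12.5%.
- r = 0.9, s = 0.5: 1.00 to 0.95, a cut of 5%.

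The means over days shrink in the same way. For days 2-5 with r = 0.8, s = 0.6 and later samples correlating 0.8 among themselves, the mean of the later samples has variance (1 + 3 × 0.8)/4 = 0.85. The change goes from 0.85 + 1 − 1.2 = 0.65 to 0.85 + 0.9 − 1.2 = 0.55, a cut of 15% instead of 40%.

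**If the planned baseline already averages the two Visit 1 samples.** Adding Day 1 as a third sample, under equal correlation:
- m = 1: 1.500 to 1.333, a cut of 11%.
- m = 4: 0.750 to 0.583, a cut of 22%.
- m = 5: 0.700 to 0.533, a cut of 24%.

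If Day 1 replaced the videoconference sample instead, b would stay at 2 and this formula would show no gain. The benefit would then lie only in comparing live with live.

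**Where the gain falls.** One baseline is subtracted from every day within a task, so it cancels from differences between days. The group-by-day interaction is unchanged; the gain is in the group main effect and the single-day comparisons.

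**The case against.** The strongest answer is that the SAP sentence is correct as it stands. It omits Day 1 from one analysis, as an outcome, and a carry-over test should do that. A reader might infer that the sample is thrown away. The documents do not say so; they simply give it no use.

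Visit 1 also holds two speech samples, so the baseline may be more than one reading. This stands, and it lowers the gain as shown above. However, one of the two is by videoconference, where the protocol expects more stuttering, and the training samples are live only. Visit 1 therefore gives one like-for-like live sample.

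The change of setting is possible, not certain: protocol section 4 allows the live baseline at home or office, while section 6.4 puts Visit 1 at OHBA. The familiarity argument is weak too. The protocol's remark concerns a first meeting, and Visit 1 follows a videoconference screening and a face-to-face appointment.

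A reader might also want the averaged baseline for the 1-week reading and conversation outcomes. The documents do not support that. Visits 1 and 7 are both placed at OHBA, so Visit 1 is the matched reference. The SAP also analyses 1, 6 and 12 weeks in one ANOVA, and a different baseline at one level would confound time with baseline definition.

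Finally, the training-day assessment is described as short, so its reliability may not equal that of Visit 1. The SAP plans nonparametric methods for non-normal variables, so variance ratios are only a guide.

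**Conclusion.** The point holds for the two exploratory training-week analyses and no further. An untreated live sample is collected and has no planned use, and the baseline subtracted in those analyses appears to be Visit 1 alone. Under equal variance and equal correlation, using the sample cuts the variance of change by 25% at one time point, 40% for the mean of days 2-5 and 42% for days 1-5. These are upper-end figures; the less favourable cases above are just as consistent with the documents.

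It would be wrong to conclude that the tDCS-sham comparison is biased. Both arms share the baseline procedure, so a shift of place or familiarity affects both unless setting differs by arm, and nothing in the documents suggests that it does. What is lost is precision and a clean reading of within-group change. Severity is minor: the SSI-4 primary outcome and the secondary follow-up outcomes are unaffected.

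**What to change.** - In the SAP, for the post-session days 1-5 and pre-session days 2-5 analyses only, define baseline % disfluent syllables as the mean of the Visit 1 live sample and the Day 1 pre-intervention live sample, separately for reading and conversation.
- Report the same analyses with the Visit 1 live sample alone as a sensitivity analysis. Averaging removes only half of any common shift of setting, so the two results should be read together.
- Keep Day 1 pre-session out of the outcome time points, as now.
- Keep one common Visit 1 baseline for the 1-, 6- and 12-week secondary outcomes, and state whether it is the live sample, the videoconference sample or both.
- Reconcile protocol sections 4 and 6.4 on where the live baseline takes place, and record the setting of each sample.

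The cost is wording, settled before unblinding; no new recording, scoring or visit is needed. There are two small downsides. The training-week baseline will differ from the follow-up baseline, so the two sets of change scores are not on an identical reference. A participant missing one of the two samples would have a baseline from the other alone.
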